A multi-center collaboration model will be adopted for the prospective cohort. ① Prospective Observational Cohort: A total of 1,000 patients will be consecutively enrolled from 10 to 15 medical centers. Pathological slides will be collected for digital scanning, and preoperative imaging data will be imported into the model. No clinical intervention will be conducted; only model predictions and actual clinical outcomes will be recorded to evaluate the model's performance in real clinical settings. ② Prospective Interventional Cohort: A randomized controlled trial will be carried out in 3 to 5 medical centers with a planned enrollment of 600 patients. After obtaining patients' informed consent, patients will be randomly assigned to the intervention group (AI model-assisted decision-making) and the control group (standard clinical decision-making). Physicians in the intervention group will formulate treatment plans with reference to the optimal treatment regimens predicted by the AI model; the control group will receive routine treatment. Clinical outcomes will be compared between the two groups to provide high-level evidence for the clinical utility of the model.

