3.3 Evaluation Index System (Algorithm Performance, Clinical Utility, System Stability)

This study comprehensively evaluates the overall value of the AI model from three dimensions: algorithm performance, clinical utility and system stability.

Evaluation of Algorithm Performance

Conducted mainly during model development and validation, quantitative indicators are used to objectively assess the accuracy and robustness of the tumor immune microenvironment identification model and treatment response prediction model.

For the tumor immune microenvironment identification model: At the pixel level, Dice Similarity Coefficient (DSC) is used to evaluate the coincidence degree between segmentation results and expert annotations, and Intersection over Union (IoU) is adopted as a supplementary indicator. At the regional level, Precision, Recall and F1-Score are used to evaluate the recognition performance of specific components in the immune microenvironment.

For the treatment response prediction model: Area Under the Receiver Operating Characteristic Curve (AUC-ROC) is used to evaluate the binary classification ability of the model, and macro-average and micro-average AUC values are calculated. Accuracy, Precision, Recall and F1-Score calculated based on the confusion matrix are used to evaluate the performance of multi-classification tasks. Calibration Curve and Brier Score are used to assess the accuracy of predicted probabilities.

Evaluation of Clinical Utility

Conducted in the prospective study phase, focusing on evaluating the actual impact of the model on clinical decision-making and patient prognosis.

Primary clinical endpoints: Relapse-Free Survival (RFS), defined as the time from randomization to tumor recurrence or death from any cause. The Kaplan-Meier method is used for survival analysis, the Log-rank test is adopted for inter-group comparison, and the Hazard Ratio (HR) and its 95% confidence interval are calculated. Overall Survival (OS), defined as the time from randomization to death from any cause, is analyzed using the same statistical methods.

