3.5 Bias Control and Fairness

A multi-level and systematic strategy is adopted to strictly control various potential biases in the study and ensure the scientificity and reliability of research results.

Bias control in study design phase: Standardized inclusion and exclusion criteria are formulated to control selection bias. In multi-center studies, all centers are required to adopt a unified patient screening process. Selection bias is assessed by comparing the basic characteristics of enrolled and unenrolled patients. For the prospective interventional study, central randomization (block randomization stratified by center) is used to assign patients to the AI-assisted decision-making group or standard treatment group to ensure balanced baseline characteristics between groups.

Bias control in data collection and processing phase: Strict blinding principles are implemented to reduce information bias and measurement bias. For pathological image annotation, at least two senior pathologists conduct independent annotations without access to any clinical outcomes of patients, and discrepancies are arbitrated by a third expert to establish high-quality gold standards. During model development, algorithm developers are prohibited from accessing data of subsequent validation sets to avoid overfitting caused by manual tuning. An independent clinical endpoint adjudication committee is established in the endpoint evaluation phase. Committee members are blinded to patient grouping information and AI prediction results, and judge tumor recurrence and survival events objectively according to established criteria to minimize assessment bias.

Bias control in algorithm development and validation phase for AI-specific biases: For spectrum bias, slide images scanned by different devices and stained with different procedures from multiple medical centers are collected. Color normalization techniques (such as the Macenko method) are adopted in the preprocessing phase to reduce the impact of staining differences. Multi-center and large-sample external validation is conducted to evaluate and correct the performance differences of the model across different populations and devices so as to control measurement bias. In addition to dividing independent validation sets, regularization and Dropout technologies are applied to prevent overfitting. Cross-validation and Bootstrap sampling results are used when evaluating model performance.

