Fairness assessment: Comprehensive fairness evaluation is carried out to analyze whether there are significant differences in model performance across subgroups divided by demographic characteristics (gender, age) and clinical characteristics (tumor stage, etiology, liver function classification). Core evaluation indicators include inter-group AUC difference, balanced odds and fairness metrics for sensitive attributes. If performance discrimination of the model is found in specific subgroups, algorithm correction will be performed to ensure the fairness of algorithm decisions. All fairness evaluation results will be fully disclosed in the research report.

Bias control in statistical analysis phase: Multivariate Cox regression model and Logistic regression model are used to adjust for known prognostic factors (such as TNM stage, vascular invasion and AFP level) to accurately estimate the independent predictive efficacy of the AI model and control potential residual confounding bias.

3.6 Data Governance System (Data Collection, Transmission, Storage Security Control; Full-chain Data Recording)

A sound data governance system is established to ensure the quality, security and compliance of data throughout the research process, covering all links including data collection, transmission, storage, processing, analysis and archiving, forming a complete data management closed loop.

Standardized data collection: Detailed Standard Operating Procedures (SOPs) for data collection are formulated to clarify the definition, format and collection specifications of all types of data. Structured electronic Case Report Forms (eCRFs) are used for clinical data collection with built-in logic verification and range check functions to ensure the accuracy and completeness of data collection. Pathological image data collection follows digital scanning standards with a unified scanning resolution of 0.25 μ m/pixel and file format of SVS. Equipment calibration and quality control tests are conducted before each batch of scanning. Laboratory test data are directly collected by docking with the Laboratory Information System (LIS) to avoid manual transcription errors.

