Random (MCAR); multiple imputation is used for data Missing at Random (MAR); selection models are applied for data Missing Not at Random (MNAR). Sensitivity analysis is conducted to compare results obtained by different missing data processing methods.

Definition of statistical analysis datasets:

Full Analysis Set (FAS): Includes all randomized patients who received at least one efficacy assessment, analyzed according to the Intention-To-Treat (ITT) principle.

Per-Protocol Set (PPS): Includes patients who fully complied with the research protocol, excluding patients with major protocol violations.

Safety Set (SS): Includes all patients who received at least one treatment, used for safety evaluation.

Primary analysis is based on the FAS, and the PPS is used for sensitivity analysis to verify the robustness of results.

Statistical methods for primary outcome indicators: For categorical variables (such as treatment response grouping), weighted F1-score and macro-average AUC are taken as main evaluation indicators, and Cohen's Kappa coefficient is used to assess the consistency between model predictions and actual clinical conditions. For survival data (RFS and OS), the Kaplan-Meier method is used to draw survival curves, the Log-rank test is used for inter-group comparison, and the Cox proportional hazards regression model is established to calculate the Hazard Ratio (HR) and its 95% confidence interval while adjusting for potential confounding factors such as age, gender and TNM stage.

Statistical methods for secondary outcome indicators: Decision Curve Analysis (DCA) is used to evaluate the clinical net benefit of the model. Calibration Curve and Brier Score are used to assess the accuracy of predicted probabilities. Repeated-measures Analysis of Variance is used for inter-group comparison of continuous variables. The Mann-Whitney U test is adopted for ordinal variables such as physician adherence and decision confidence scale scores.

Algorithm stability evaluation: Bootstrap sampling (1,000 repetitions) is used to calculate the 95% confidence interval of model performance indicators for stability assessment. SHapley Additive exPlanations (SHAP) values are used to analyze feature importance and improve model interpretability. Intraclass Correlation Coefficient (ICC) is calculated to evaluate the consistency of the model across different centers; $ICC > 0.75$ is regarded as good consistency.

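### Randomisation is stratified by centre, but the stated log-rank test names no strata and the Cox covariates omit centre; the likely cost is a conservative test with a nil to modest loss of power

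*Protocol*

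**What the plan says.** - **Design.** Protocol 3.1 (Part Two): "A randomized controlled trial will be carried out in 3 to 5 medical centers with a planned enrollment of 600 patients". Section 3.5: "central randomization (block randomization stratified by center) is used to assign patients" to the two arms.
- **Primary test.** Section 3.3, for RFS: "the Log-rank test is adopted for inter-group comparison". Section 3.8 repeats it: "the Log-rank test is used for inter-group comparison". Neither names strata.
- **Hazard ratio.** Section 3.8 takes it from a Cox model fitted "while adjusting for potential confounding factors such as age, gender and TNM stage". Centre is not named. In 3.8 centre appears only in an intraclass correlation for the consistency of the AI model across centres.
- **A further list.** The paragraph of 3.5 on bias control at the analysis stage says that Cox and logistic models will "adjust for known prognostic factors (such as TNM stage, vascular invasion and AFP level"), and gives the purpose as "to accurately estimate the independent predictive efficacy of the AI model and control potential residual confounding bias".

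**The concern.** Blocking within centre keeps the two arms balanced in every centre, so differences in prognosis between centres are largely removed from the treatment comparison. A log-rank test that ignores centre still uses a variance that allows for chance imbalance between centres. That variance is too large whenever centres differ in recurrence risk, and the test then rejects less often than its nominal 5%. Pooling patients with different underlying hazards also pulls the estimated hazard ratio towards 1. Both effects cost power.

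Differences between centres are plausible here: the controls receive whatever is routine locally, and section 3.1 recognises four adjuvant regimens. The trial is planned at 80% power on 200 events, so at that event count any loss takes it below its target.

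**Working it through.** **Inputs from Protocol 3.4.2:** control 12-month RFS 65%, AI-assisted arm 75%, HR 0.67, alpha 0.05 (two-sided, from 3.8), power 80%, 18 months accrual, 12 months follow-up, 10% dropout, 200 events, 600 patients allocated 300 and 300. From 3.1: 3 to 5 centres.

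**Step 1: reproduce the plan's own figure.**
- HR = ln(0.75)/ln(0.65) = 0.668, which agrees with 0.67.
- Schoenfeld: events = 4(1.960 + 0.842)² / (ln 0.67)² = 31.4/0.1604, giving 196.
- Freedman: events = (1.960 + 0.842)² × (1.67/0.33)², giving 202.
- Power at 200 events: Φ(√200/2 × 0.4005 − 1.960) = Φ(0.872) = 80.8%.

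The stated 200 events reproduce.

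**Step 2: what ignoring centre costs at that design.** The simulation used 600 patients in 3 or 5 equal centres (200 or 120 each), blocks of 4 within centre, exponential RFS with 65% of controls relapse-free at 12 months, uniform accrual over 18 months, and analysis at the 200th event. There were 8,000 trials per cell, with Monte Carlo error of about 0.25 points for type I error and 0.45 points for power. Dropout was taken as 10% per year, because the protocol gives no time unit.

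The SD of the centre log hazards is an assumption, ranged over 0 to 0.6. The hazard ratio between a centre one SD above the mean and one SD below it is exp(2 × SD): 1.5 at 0.2, 2.2 at 0.4 and 3.3 at 0.6.

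| Centres | SD | Type I error, unstratified / stratified (%) | Power, unstratified / stratified (%) | Difference in power (points) |
|---|---|---|---|---|
| 3 | 0 | 5.4 / 5.5 | 80.8 / 80.5 | −0.3 |
| 3 | 0.2 | 4.9 / 4.9 | 80.5 / 81.0 | 0.5 |
| 3 | 0.4 | 4.7 / 5.4 | 78.5 / 80.4 | 1.9 |
| 3 | 0.6 | 3.9 / 4.9 | 76.4 / 80.5 | 4.1 |
| 5 | 0 | 4.7 / 4.7 | 80.1 / 80.0 | −0.1 |
| 5 | 0.2 | 5.0 / 5.2 | 79.5 / 79.8 | 0.3 |
| 5 | 0.4 | 4.1 / 4.8 | 79.0 / 80.9 | 1.9 |
| 5 | 0.6 | 3.5 / 4.6 | 75.5 / 79.9 | 4.4 |

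Measured against the 80% target instead of the stratified test, the losses are 1.0 to 1.5 points at SD 0.4 and 3.6 to 4.5 points at SD 0.6. Taking both measures and the Monte Carlo error together, the loss is about nothing at SD 0 to 0.2, about 1 to 2 points at 0.4, and about 3 to 4.5 points at 0.6.

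**Step 3: sensitivity to when the analysis is done.** If all patients are followed until 12 months after accrual closes, the average event probability under exponential RFS is 0.456. That gives 246 events from 540 evaluable patients or 274 from 600. A simulation at that calendar cut-off (6,000 trials per cell) gave about 89% power with no heterogeneity. At SD 0.8 the unstratified test still had 81 to 82%, against 90 to 91% stratified, with unstratified type I error of 2.4 to 2.6%.

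**The case against.** **The plan does not choose an unstratified test.** It says log-rank and is silent on strata, its Cox covariates are given as examples, and a separate SAP may settle both. This is fair: centre is unnamed, not excluded. But section 3.8 is itself headed as the statistical analysis plan and sets out test, model and covariates for the primary outcome. As written, they do not follow the randomisation.

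**The loss may be nil.** This stands. It depends on heterogeneity that the protocol does not quantify, and unified screening and blinded adjudication may limit some of it. An SD of 0.6 already means a 3.3-fold spread in hazard. Any error is conservative, so the risk of a false positive does not rise.

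**Stronger readings the documents do not support.**
- A reader might infer a serious shortfall in power. Simulating HR 0.75 with about 250 events and SDs of 0.6 and 0.9 does give 61% and 55% unstratified. But the stratified test then reaches only 68 to 69%, so part of the gap from 80% comes from the weaker effect. The protocol's effect is HR 0.67, and an SD of 0.9 implies a six-fold spread (exp 1.8).
- A reader might infer that the differing covariate lists in 3.5 and 3.8 contradict each other and weaken the primary test. A log-rank test uses no covariates, so they cannot affect it. Both lists are illustrative, and the one in 3.5 is tied to the predictive value of the AI model, not clearly to the randomised comparison. Closing the list is detail that an SAP may supply.

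**Conclusion.** The point holds in a limited form. The protocol stratifies randomisation by centre and does not carry centre into the stated log-rank test or the named Cox covariates. If the test is run as written, it is valid but conservative to the extent that centres differ in recurrence risk. At 200 events the loss lies between nil and about 4.5 points of power over the assumed SD range of 0 to 0.6, with type I error of about 3.5 to 4% at the top of that range. If follow-up runs to the calendar cut-off and yields more events, power stays above 80% even at SD 0.8, and the issue is lost efficiency, not a missed target. The sizes rest on the assumed SD, exponential RFS, equal centres and dropout of 10% per year. The direction of the effect does not depend on the particular SD, provided centres differ.

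**What to change.** In section 3.8, and where 3.3 describes the RFS comparison, make the primary test a log-rank test stratified by centre, and report the hazard ratio and its 95% confidence interval from a Cox model stratified by centre.

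Centre is already known for every randomised patient, so there is no data cost. With 3 to 5 centres of roughly 120 to 200 patients, the strata are large. The simulation shows no measurable loss of power if centres turn out alike, and the required number of events does not change.

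Adding vascular invasion and AFP to the Cox adjustment in 3.8 is optional; the prospective eligibility criteria in 3.1 already require both to be available.

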7.1 Common Risks of Interventional Therapy

Postembolization syndrome: fever, pain, nausea and vomiting;

Liver function injury: transient transaminitis, jaundice and ascites; severe cases may lead to liver failure. Embolization-related complications: cholecystitis, gastroduodenal erosion or ulcer, splenic infarction, etc.;

Puncture-related complications: hematoma at the puncture site, pseudoaneurysm and vascular injury;

Others: renal function injury, allergic reaction, infection, etc.

7.2 Common Risks of Targeted Drug Therapy

Common adverse reactions: hypertension, hand-foot skin reaction (redness, desquamation and pain of hands and feet), diarrhea, decreased appetite, fatigue, weight loss, abnormal thyroid function, proteinuria, etc.;

Hematological toxicity: thrombocytopenia, leukopenia and increased bleeding risk;

Severe but rare adverse reactions: cardiac dysfunction, arterial thromboembolism, gastrointestinal perforation, impaired wound healing, etc.

7.3 Preventive Measures

Standard operating procedures will be strictly followed. The physical condition of subjects will be comprehensively evaluated before treatment. Subjects will be closely monitored during and after treatment. Routine blood tests, liver and kidney function tests, electrocardiograms and other examinations will be performed regularly to detect and manage any possible adverse reactions in a timely manner. Complete emergency plans and rescue measures are prepared, and detailed guidelines for adverse reaction management (such as management of hypertension and skin reactions) are provided for researchers.

In case of severe intolerable adverse events (SAE), the research physician will reduce the drug dose, suspend or permanently terminate the study treatment in accordance with the protocol, and provide necessary medical support for the subjects. All adverse events will be recorded in the Case Report Form. The Ethics Committee, clinical trial institution and sponsor shall be notified immediately. Relevant national and provincial drug regulatory authorities shall be reported within 24 hours. All SAEs must be reported through the internal hospital adverse event and near-miss no-fault reporting system.

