Research Title: Construction and Clinical Validation of a Predictive
Model for Postoperative Adjuvant Therapy in Hepatocellular Carcinoma
Based on Whole-Slide Digital Pathological Images and Deep Learning

NCT Number: NCT07417800

Document date: 2025/10/24

Research Protocol

Study Background

Hepatocellular Carcinoma (HCC) is one of the most common malignant tumors worldwide, ranking sixth in incidence and third in mortality globally, causing approximately 480,000 deaths each year. China accounts for more than 45% of global HCC cases, resulting in an extremely heavy disease burden. Curative surgical resection is the primary approach to achieve long-term survival for patients with early-stage HCC. However, the postoperative recurrence rate reaches 50%–70% within five years after surgery, which seriously impairs patient prognosis. Postoperative adjuvant therapy has become a key strategy to delay tumor recurrence and improve survival outcomes. Transarterial Chemoembolization (TACE) and Tyrosine Kinase Inhibitors (TKIs), such as sorafenib and lenvatinib, are widely applied for patients at high recurrence risk after surgery.

Nevertheless, both treatment modalities have notable limitations. The objective response rate of TACE is merely 50%–60%; a considerable number of patients fail to benefit from this therapy and may suffer from treatment-induced liver function injury. Although TKIs can prolong recurrence-free survival (RFS) by 3 to 5 months in high-risk postoperative HCC patients, the treatment response rate is less than 20% in unselected populations. Additionally, the incidence of Grade 3–4 adverse events including hypertension, hand-foot skin reaction and proteinuria exceeds 50%, leading to treatment discontinuation in around 20% of patients due to intolerable toxicities. Currently, there is a lack of efficient and reliable biomarker systems to identify patients who may benefit from treatment. Clinical treatment decisions still rely on empirical judgment based on conventional pathological features such as tumor size and vascular invasion, resulting in insufficient individualized treatment, wasted medical resources and additional treatment burdens on patients.

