Data governance organizational structure: A data governance committee is set up to formulate data management policies. Dedicated data administrators are assigned to be responsible for daily data management. A data quality supervision team conducts regular data quality inspections. All researchers are required to receive and pass data management training to ensure the implementation of standardized data management.

3.7 Adverse Events (Specific Definition, Classification, Reporting Methods and Treatment Measures for Adverse Events/Serious Adverse Events)

Adverse events in this study refer to any negative medical outcomes related to AI-assisted decision-making, which are divided into three grades:

Grade 1 (Mild): AI recommendations lead to minor inconvenience or reversible additional examinations without long-term impacts;

Grade 2 (Moderate): AI recommendations result in inappropriate treatment regimens, which require medical intervention for correction without permanent damage;

Grade 3 (Severe): AI recommendations lead to misdiagnosis and mistreatment, causing permanent functional damage or significant shortening of survival time.

Once an adverse event occurs, the clinical center shall report it to the research safety monitoring committee through the online system within 24 hours. The committee consists of experts in hepatology, oncology, pathology and medical ethics. Treatment measures include immediately suspending the use of the AI system, organizing experts to assess the cause of the event, determining the correlation with the AI system, and formulating corrective measures. All adverse events will be fully recorded and included in the final research report.

3.8 Statistical Analysis Plan (Methods for Missing Data Processing, Definition and Selection of Statistical Analysis Datasets, Statistical Methods for Comparing Primary and Secondary Outcome Indicators, Algorithm Stability Evaluation)

R (Version 4.2.0), Python (Version 3.9) and SPSS (Version 26.0) software will be used for all statistical analyses. All statistical tests are two-sided with a significance level of $\alpha=0.05$.

Missing data processing: Multiple imputation method is adopted. For continuous variables, the Multiple Imputation by Chained Equations (MICE) is used to create 5 imputed datasets for combined analysis. Mode imputation is applied for categorical variables. The missing data mechanism will be tested: Complete Case Analysis is adopted for data Missing Completely at

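### Sections 3.7 and 7.3 give adverse event different meanings, so toxicity not attributed to the AI, including essentially all control-arm toxicity, has no stated route to the safety committee

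*Protocol*

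**What the plan says.** **Protocol Section 3.7 (Adverse Events).** The heading announces "Specific Definition, Classification, Reporting Methods and Treatment Measures for Adverse Events/Serious Adverse Events". The text then sets the meaning of the term for the whole study: "Adverse events in this study refer to any negative medical outcomes related to AI-assisted decision-making, which are divided into three grades". Grade 2 (Moderate) is where "AI recommendations result in inappropriate treatment regimens, which require medical intervention for correction without permanent damage". Grade 3 (Severe) is where "AI recommendations lead to misdiagnosis and mistreatment, causing permanent functional damage or significant shortening of survival time". When such an event occurs, "the clinical center shall report it to the research safety monitoring committee through the online system within 24 hours". The response is aimed at the software: "Treatment measures include immediately suspending the use of the AI system". The body of the section does not mention or define a serious adverse event.

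**Protocol Section 7.3 (Preventive Measures).** This follows the lists of procedure risks (7.1) and targeted-drug risks (7.2). It uses adverse event for those toxicities and says: "In case of severe intolerable adverse events (SAE), the research physician will reduce the drug dose, suspend or permanently terminate the study treatment". This is the only place where the abbreviation SAE is spelled out. The section has all adverse events recorded in the case report form. It calls for immediate notice to the ethics committee, the institution and the sponsor, a regulatory report within 24 hours, and entry of all SAEs in the hospital's internal system.

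**Elsewhere in the protocol.** Section 3.1, Part Two, gives the control arm routine treatment, while physicians in the other arm plan treatment with reference to the AI's recommendation. Section 3.8 defines the Safety Set as all patients who received at least one treatment. It mentions the DSMB only as the body that approves sample size re-estimation.

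**The concern.** A randomised comparison of safety needs the same kind of event to be defined, collected and passed on in the same way in both arms. Here the study-wide definition depends on a link to an AI recommendation, and only one arm receives one. The drug-safety section, which could have filled the gap, uses a different meaning of the same term and a different list of recipients.

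Two things are at stake. The first is oversight: the committee set up to watch safety may receive only those harms that a site blames on the AI. It would then have no control-arm rate against which to judge the regimens that the AI steers patients towards. The second is consistency: sites have to classify and route events under two rules that do not match.

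**Working it through.** No sample size, power or event count is in dispute, so the check is a comparison of the two sections.

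| Item | Section 3.7 | Section 7.3 |
|---|---|---|
| What is an adverse event | Harm related to AI-assisted decisions | Drug and procedure toxicity, by context |
| Classification | Three grades; Severe needs permanent damage or clearly shortened survival | One label, SAE, built on intensity and tolerability; no grade or outcome criterion |
| SAE definition | Promised in the heading, absent from the text | Only the spelled-out abbreviation |
| Recipients | Research safety monitoring committee | Ethics committee, institution, sponsor, regulators, hospital system |
| Action directed at | The AI system | The drug |

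**Step 1: a control-arm toxicity.** No AI recommendation informs treatment in this arm, so the event can hardly be related to AI-assisted decision-making. It is not an adverse event under Section 3.7 and does not go to the committee. Section 7.3 covers it but lists neither that committee nor the DSMB. No stated route remains.

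**Step 2: an AI-arm toxicity that the site does not attribute to the AI.** The result is the same.

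**Step 3: an AI-arm toxicity attributed to the AI.** Section 3.7 applies, and the event reaches the committee within 24 hours whatever its grade. Comparing this with Step 1, harm under the Section 3.7 definition can arise in essentially one arm only. The Safety Set contains both arms, so a between-arm comparison on that definition is asymmetric by construction.

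**Step 4: an intolerable but reversible toxicity attributed to an inappropriate AI recommendation and needing medical intervention.** It meets Grade 2 (Moderate) in Section 3.7 and can be an SAE in Section 7.3. The conflict arises only with all of these conditions. Without the AI attribution, Section 3.7 does not grade the event at all.

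**Step 5: the notification trigger in Section 7.3.** Only the dose/stopping sentence and the hospital-system sentence concern SAEs by name. The sentences on immediate notice and the 24-hour regulatory report come after the one on recording all adverse events, and they do not say which events they cover. SAE is the natural reading, but all adverse events is a possible one.

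**Step 6: scale, for illustration only.** Section 3.4.2 gives 600 patients, 300 per group, so 300/600 = 50% of randomised patients fall under Step 1. The share of controls on a TKI is not stated; assume 25% to 75%:

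- 300 × 0.25 = 75 and 300 × 0.75 = 225 patients on a TKI.
- The Study Background reports toxicity "leading to treatment discontinuation in around 20% of patients due to intolerable toxicities". This gives 75 × 0.20 = 15 to 225 × 0.20 = 45 patients.
- The same section puts Grade 3–4 events above 50%. This gives more than 75 × 0.50 ≈ 38 to 225 × 0.50 ≈ 113 patients.

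These are patients with toxicity, not counts of SAEs or of reports. TACE toxicity would come on top.

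**The case against.** The best defence is that the sections are complementary: Section 3.7 handles harm from the software and Section 7 handles harm from treatment. All adverse events go in the case report form, the Safety Set includes every treated patient, and a DSMB exists, so toxicity can still be evaluated. The label in Section 7.3 may be no more than a loose translation of serious.

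Part of this stands. Toxicity data will probably be collected, and the point is not that they are lost. But Section 3.7 says what adverse events are in this study, without limiting itself to the software, so the two uses do collide. The DSMB's only stated task is sample size re-estimation. A translation slip would explain the label, but not the missing definition, the conflicting classification or the recipient list. Nor is this detail that can wait for the SAP: the protocol announces the definition and the text beneath does not supply it.

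A reader might infer more than the documents support:

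- **That serious but tolerated events escape expedited reporting.** This holds only if the notification sentences are confined to SAEs as Section 7.3 words them. On the other reading of Step 5, every adverse event is notified.
- **That any reversible complication after AI-recommended treatment is Moderate.** Grade 2 also requires the recommended regimen to have been inappropriate. A known complication can follow an appropriate one.
- **That the 20% and 50% background rates bracket the number of SAEs.** Section 7.3 requires severity and intolerability together, and the protocol never ties its wording to background Grade 3–4.
- **That the protocol has no dose or stopping rule for Section 7.3 to refer to.** The text at hand runs from Section 3.9 to 7.1, and Section 7.3 mentions management guidelines for researchers, so absence cannot be asserted.

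**Conclusion.** The point holds in this form. Sections 3.7 and 7.3 use one term for two sets of events, no SAE definition based on seriousness is given, and toxicity not attributed to the AI has no stated path to the research safety monitoring committee. This affects essentially all toxicity in the control arm, half of the randomised patients, and the unattributed part in the AI arm. A safety comparison under Section 3.7 is therefore asymmetric. The double classification in Step 4 is real but narrow. The unclear notification trigger is a separate drafting fault.

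The conclusion rests on the wording alone and on reading the Section 3.7 definition as study-wide, as it states. It does not depend on the assumed TKI share. It should be corrected before the randomised cohort enrols, because events classified under two rules are hard to re-sort afterwards.

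**What to change.** Reconcile Sections 3.7 and 7.3 by amendment:

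1. Give one definition of adverse event and one of serious adverse event, the latter based on seriousness of outcome. Apply both to both arms regardless of AI attribution. Record relatedness to the AI as a separate attribute, so that the Section 3.7 grading of AI-related harm can be kept alongside.
2. State which events trigger the immediate and the 24-hour notifications in Section 7.3.
3. Send SAEs from both arms to the existing research safety monitoring committee, in addition to the recipients in Section 7.3.

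Section 7.3 also makes dose changes and stopping follow the protocol, while Section 3.1, Part Two, leaves treatment to routine care in one arm and to the physician's plan in the other. The sponsor must reconcile these passages; no clinical rule is proposed here.

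The cost is wording in two sections and one added recipient on the reporting form. The downside is somewhat more case flow to a committee that already exists.
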